14.1.2.2 Demographics and Baseline Characteristics

14.1.3 Summary of Concomitant Medications and Non-Drug Therapies

14.1.4 Extent of Exposure and Percent Compliance

PK Population

14.1.5 Summary of Plasma Concentrations of CX-8998 and Metabolites

Safety – Safety Population

14.3.1.1 Summary of Treatment-Emergent Adverse Events

14.3.1.2 Treatment-Emergent Adverse Events by System Organ Class, Preferred Term, and Greatest Severity

14.3.1.3 Treatment-Emergent Adverse Events Related to Study Drug by System Organ Class and Preferred Term

14.3.1.4 Treatment-Emergent Adverse Events by CX-8998 Dose Administered, System Organ Class, and Preferred Term

14.3.2.1 Treatment-Emergent Serious Adverse Events by System Organ Class and Preferred Term

14.3.2.2 Treatment-Emergent Adverse Events Leading to the Discontinuation of Study Drug by System Organ Class and Preferred Term

14.3.2.3 Treatment-Emergent Adverse Events of Special Interest by System Organ Classification and Preferred Term

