**Figure 6 Schematic of Study Design**

### **3.3 Endpoints**

#### **3.3.1 Primary Endpoint**

Safety and tolerability endpoints:

- Treatment-emergent adverse events (TEAE),
- Changes from baseline in QTcF and other ECG parameters,
- Changes from baseline in clinical safety laboratory assessments (clinical chemistry, hematology, and urinalysis),
- Changes from baseline in vital signs,
- Number (%) of subjects who did not complete the study due to TEAEs
- Number (%) of subjects with SAEs
- Number (%) of subjects with adverse events of special interest (AESI):
  - Increased seizure frequency
  - New seizure types
  - Status epilepticus
- Columbia-Suicide Severity Rating Scale (C-SSRS)
- University of Miami Parkinson's Disease Hallucinations Questionnaire (UM-PDHQ)

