## **10.2.2 Collection and Rating of Adverse Events**

All AEs, irrespective of the relatedness to the study drug, will be captured from the time the ICF is signed through the telephone safety check on Day 33. SAEs will be reported up to 30 days after the last dose of study drug. A follow-up phone call will be made 30 days after the last dose of study drug for evaluation of any SAEs. In case of an SAE, an SAE Report Form must be completed and transmitted to the sponsor or designee within 24 hours.

Overdoses and medication errors in the presence of clinical consequences should be recorded as AEs. The clinical consequence should be reported as “[enter AE] due to overdose.” See [Section 4.7](#) for overdose management.

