16. A single lead EEG will be bipolarly recorded for 5 days using a wearable EEG patch (Epitel device). The EEG recording will be centrally evaluated by a qualified rater. Subjects will be trained in the use of the device by site personnel and will replace the EEG patch every 7 days. Subjects will receive the device at screening. On Days 8 and 20, the nurse who conducts the home visit will check positioning of the device. The device will be returned on the Day 26 clinic visit. This assessment is based on device availability.
17. The "lifetime" version of the C-SSRS will be used at screening, and the "since last visit" version will be completed at all other visits.
18. The UM-PDHQ is a 20-item clinician-administered questionnaire that quantitatively and qualitatively assesses hallucinations. The UM-PDHQ will be completed for any subject who reports hallucinations.
19. All AEs, irrespective of the relatedness to the study drug, will be captured from the time the ICF is signed through the EOS visit. All AEs should be followed until resolution, for 30 days after onset, for 30 days after the last dose of study drug, until the subject is lost to follow-up, or the subject withdraws consent, whichever occurs first. Serious adverse events (SAEs) will be reported up to 30 days after the last dose of study drug. A follow-up phone call will be made 30 days after the last dose of study drug for evaluation of any SAEs.
20. Concomitant medications and adverse events will be recorded by the visiting nurse on Days 8 and 20.

21. Study drug will be administered in the clinic on the morning of Day 1 and Day 26. Study drug will be administered on an outpatient basis on the evening of Day 1 and Day 26 and on the morning of Day 27.
22. Drug compliance will be assessed by a remote mobile technology monitoring application (AiCure).
23. Evaluation of drug compliance and dosing accuracy will be assessed by the visiting nurse.
24. Subjects will return all remaining study drug (including empty bottles) to the site via a prepaid mailer.

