3.3.7. Definitions and Terminology

Age

The age of a subject is defined as the number of whole years between the subject's birth date and the date of informed consent.

Day 1 (Baseline)

Day 1 is the earliest day that study drug is initiated.

Study Day

Study Day is defined relative to Day 1 as follows: Study Day = Date of event – Date of Day 1 +1*(1 if date of event \geq Date of Day 1, 0 otherwise).

Study Visit

Study Visit is the nominal visit as recorded on the eCRF.

Baseline Value

For purposes of analysis, the baseline value is defined as the last non-missing value obtained prior to initiation of study drug.

Change from Baseline

Change from baseline for a given endpoint is defined as the Study Day X value minus the baseline value.

Percent Change from Baseline

Percent change from baseline for a given endpoint is defined as the Study Day X value minus the baseline value, quantity divided by the baseline value, multiplied by 100.

$$\text{Percent Change from Baseline} = (\text{Study Day X} - \text{Baseline})/\text{Baseline} * 100$$

Days on Study

Days on study is defined as the number of days from the date of study drug initiation to the final study visit (includes in home or in clinic assessments).

Completer

A subject is defined as a completer if he/she completes the Day 26 EEG and Day 27 dosing regardless of completing the Day 33 visit.

Treatment Period

The treatment period is the period during which a subject receives study drug (i.e., first dose through Day 27).

Days on Study Drug

Days on study drug is defined as the number of days in the treatment period. The date of the last dose of study drug as recorded on the End of Study Visit form or from the AICure electronic data transfer.

Total Study Drug Expected (capsules)

The total study drug expected is defined as the total number of capsules expected to be taken as recorded from all sources and reported from the AICure system.

Total Study Drug Received (capsules)

The total study drug received is defined as the total number capsules of taken as recorded from all sources and reported from the AICure system.

Total Study Drug Received (mg)

The total study drug received (mg) amount will be multiplied by 2 for subjects receiving CX-8998 to calculate the amount of study drug received in mg (i.e., each capsule is 2 mg).

Treatment Compliance

Treatment compliance will be calculated for each subject as a percentage using the following formula:

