5.3. SAFETY AND TOLERABILITY

5.3.1. Safety and Tolerability Endpoints

The primary objective of this study is to assess the safety and tolerability of CX-8998. The following endpoints will be captured and evaluated:

- TEAEs
- changes from baseline in QTcF and other electrocardiogram (ECG) parameters
- changes from baseline in clinical safety laboratory assessments (clinical chemistry, hematology, and urinalysis)
- changes from baseline in vital signs
- number (%) of subjects who did not complete the study due to TEAE
- number (%) of subjects with SAE
- number (%) of subjects with Adverse Events of Special Interest (AESI) from the AE pages of the CRF:
 - Increased seizure frequency
 - New seizure types
 - Status epilepticus
- Columbia Suicide Severity Rating Scale (C-SSRS)
- Epworth Sleepiness Scale (ESS)

- University of Miami Parkinson's Disease Hallucinations Questionnaire (UM-PDHQ)

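### The SAP gives two conflicting ends to the treatment-emergent window, so the SAE and AESI endpoint counts are not uniquely defined for events after the last dose

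*SAP*

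**What the plan says.** **Endpoints.** Protocol 3.3.1 lists "Number (%) of subjects with SAEs". SAP 5.3.1 lists "number (%) of subjects with SAE" and "number (%) of subjects with Adverse Events of Special Interest (AESI) from the AE pages of the CRF". None of these carries a treatment-emergent qualifier, although the same lists apply one to the general AE item and to non-completion.

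**Collection.** Under SAP 1.2, footnote 19, all AEs "will be captured from the time the ICF is signed through the EOS visit", which the schedule places at Day 33. The same footnote adds: "Serious adverse events (SAEs) will be reported up to 30 days after the last dose of study drug". Protocol 10.2.2 agrees that AEs are "captured from the time the ICF is signed through the telephone safety check on Day 33".

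**Tables.** SAP Section 10 plans "14.3.2.1 Treatment-Emergent Serious Adverse Events by System Organ Class and Preferred Term". Table 14.3.2.3 does the same for AESIs, and Table 14.3.1.1 is an overall summary of TEAEs. Protocol 11.5.2 also describes its SAE summaries as treatment-emergent. Listing 16.2.7 covers adverse events by subject. SAP Section 7 declares no change to the SAE or AESI endpoints.

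**Window.** SAP 3.3.7 ties a TEAE to the treatment period and states: "The treatment period is the period during which a subject receives study drug (i.e., first dose through Day 27". SAP 5.3.2.3, which specifies the AE tables, does not cite that definition. It refers to Section 3.3.5, and the only exclusion from the tables that it names is onset before study treatment. One bullet in 3.3.5 makes any AE with onset later than the first-dose date treatment-emergent, with no closing date. That bullet stands in a section on incomplete dates, under a lead-in that presents it as an extra criterion for AEs whose start or stop date is missing.

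**The concern.** Safety is the primary objective, and two of the primary endpoints are simple counts of subjects. The endpoint wording and the collection period both reach past the last dose. The tables that must deliver those counts are restricted to a window that, on one reading, closes at the last dose. The protocol treats the later period as relevant to safety: it schedules a follow-up contact after dosing, and Section 10.4 suspends enrolment for a possibly related death within 30 days of the last dose.

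At stake is whether an SAE or AESI first seen after Day 27 enters the tabulated primary result. Two programmers could each follow the SAP and report different numbers.

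**Working it through.** The plan states no figure to reproduce. The check is day arithmetic, followed by classifying example events under each rule.

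**Inputs.** Last dose is Day 27 (SAP 1.1 and 3.3.7). AE collection ends at the Day 33 contact, with a window of ±1 day (SAP 1.2). SAE collection ends 30 days after the last dose (SAP 1.2, footnote 19). Sample size is up to 15 (SAP 3.1). Days are counted from first dose for a subject who completes dosing.

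**Days outside the tables if 3.3.7 governs.**

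- AEs, including non-serious AESIs: (33 − 27)/33 = 6/33 = 18%. With the visit window, 5 to 7 days are outside.
- SAEs: collection ends on Day 27 + 30 = Day 57, so (57 − 27)/57 = 30/57 = 53%.

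With the current protocol's last dose on Day 26, the figures are (33 − 26)/33 = 7/33 = 21% and 30/56 = 54%. The Day 26/27 difference is not an error: SAP 1.1 explains that no subject enrolled under amendments 4 and 5, so the analysis follows amendment 3.

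**Days outside if the 3.3.5 bullet governs all AEs:** none, because it has no end date.

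**Classification of example events**

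| Event | 3.3.7 alone | 3.3.5 bullet applied to all AEs | 3.3.7, plus 3.3.5 for missing dates only |
|---|---|---|---|
| SAE, onset Day 20, dates complete | in | in | in |
| AESI, onset Day 30, resolved, dates complete | out | in | out |
| SAE, onset Day 40, resolved, dates complete | out | in | out |
| AESI, onset Day 30, stop date missing | out | in | in |
| AE, onset Day −5, no worsening | out | out | out |

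The third reading is the most literal one, and it gives an odd result. Two AESIs with the same Day 30 onset are treated differently only because one has a recorded stop date.

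**Effect on the count.** If exactly one of 15 subjects has such an event and no other, reported incidence is 0/15 = 0% or 1/15 = 6.7%, depending on the rule chosen.

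**The case against.** The strongest reply is that SAP 5.3.2.3 is the operative section for the AE tables. It sends treatment emergence to 3.3.5 and excludes only pre-treatment onset. Read that way, a Day 29 SAE is counted and there is no gap. A reader who sees only 3.3.7 might infer that every event after Day 27 is missing from all tables. The documents do not support that: such events are counted if 3.3.5 governs, and those with a missing stop date meet 3.3.5 even on its narrow reading.

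This reply does not settle the matter for fully dated events. Section 3.3.5 limits its own scope to AEs with missing dates, and 3.3.7 still gives an explicit definition. Excluding events before treatment is not the same as including events after it. Table 14.3.1.4 assigns TEAEs to a dose by start date, and the SAP describes no post-dose category, which fits an on-treatment window better.

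Three further points have force:

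- Protocol 11.5.2 itself plans treatment-emergent SAE summaries, so the SAP did not narrow the protocol's analysis. The mismatch between endpoint and summary begins in the protocol.
- Listing 16.2.7 would show a late event individually, which matters with at most 15 open-label subjects. A listing does not, however, supply the number and percentage that the endpoint names.
- The 18% and 53% are shares of calendar days, not of expected events.

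**Conclusion.** The point holds as a conflict within the SAP. Two primary safety endpoints have no treatment-emergent limit, their only tables are treatment-emergent, and the SAP gives two different ends to that window. Under 3.3.7, a fully dated SAE or AESI starting after Day 27 is in no SAE or AESI table and appears only in Listing 16.2.7. Under 3.3.5 as invoked by 5.3.2.3, it is tabulated. The period in dispute is 6 of 33 AE collection days and 30 of 57 SAE collection days. One affected subject among 15 moves incidence by 6.7 percentage points.

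These figures assume a last dose on Day 27 and nominal visit days. They say nothing about how likely late events are.

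Because the AESIs are seizure events and dosing stops at the end of titration, a reader might also infer that stopping the drug worsens seizures. The available text does not show this, and the clinical safety background is blacked out. The case for a defined window does not depend on it. The plan should be changed, but this is a matter of definition and output and does not threaten the trial's validity.

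**What to change.** 1. Reconcile SAP 3.3.5, 3.3.7 and 5.3.2.3 so that one rule decides treatment emergence for fully dated AEs, and confine the 3.3.5 bullets explicitly to incomplete dates.
2. For the SAE endpoint in SAP 5.3.1, tabulate subjects with SAEs, including serious AESIs, from first dose to 30 days after the last dose.
3. For the AESI endpoint, tabulate non-serious AESIs from first dose through the Day 33 contact, and serious AESIs to 30 days after the last dose. A single Day 33 cutoff would drop serious AESIs that are collected later. Footnote the two collection periods.
4. Split each table into on-treatment and after last dose, using the last-dose date already recorded. Keep the on-treatment counts so that on-drug incidence is not diluted.
5. If only on-treatment events are intended, say so in SAP 5.3.1 and declare the restriction in Section 7.

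The cost is a few extra table columns from data already collected. No assessment or clinical rule changes.

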14.3.4.1 Summary of Hematology Assessments

14.3.4.2 Summary of Serum Chemistry Assessments

14.3.4.3 Summary of Coagulation Assessments

14.3.4.4 Summary of Urinalysis Assessments

14.3.4.5 Shift from Baseline of Laboratory Abnormalities

14.3.5.1.1 Summary of Electrocardiogram Parameters

14.3.5.1.2 Summary of Electrocardiogram Outliers

14.3.5.2.1 Summary of Respiration Rate, Temperature, and Weight

14.3.5.2.2 Summary of Blood Pressure and Pulse

14.3.5.2.3 Summary of Vital Signs Outliers

Data Listings – ITT Population

16.2.1.1 Subject Disposition

16.2.1.2 Informed Consent and Eligibility

- 16.2.2 Protocol Deviations
- 16.2.3 Reasons for Exclusion from Study Populations
- 16.2.4.1 Demographics and Baseline Characteristics
- 16.2.4.2 Medical and Surgical History
- 16.2.4.3 Prior and Concomitant Medications and Non-Drug Therapies
- 16.2.5.1 Study Drug Dose Change Log
- 16.2.5.2 AICure Dose Compliance
- 16.2.5.3 Pharmacokinetic Samples
- 16.2.6.1 Ambulatory EEG
- 16.2.6.2 Subject Diary Information
- 16.2.6.3 Seizure-Related Disability Assessment Scale
- 16.2.7 Adverse Events
 - 16.2.8.1.1 Laboratory Tests – Hematology
 - 16.2.8.1.2 Laboratory Tests – Serum Chemistry
 - 16.2.8.1.3 Laboratory Tests – Coagulation
 - 16.2.8.1.4 Laboratory Tests – Urinalysis
 - 16.2.8.1.5 Pregnancy Test
 - 16.2.8.1.6 Laboratory Tests – Other
 - 16.2.8.2 Vital Signs, Height, and Weight
 - 16.2.8.3 Physical Examination
 - 16.2.8.4 Neurological Examination
 - 16.2.8.5 Electrocardiogram
 - 16.2.9.1 Epworth Sleepiness Scale
 - 16.2.9.2 Columbia Suicide Severity Rating Scale
 - 16.2.9.3 UM-PDHQ
